8.1.3. Assessments during ctDNA surveillance

The following assessments should be conducted for all patients confirmed by ICR-CTSU as eligible for ctDNA surveillance for up to 2 years, except if a patient is allocated to the pembrolizumab treatment group (see sections 9 and 10):

- Research blood samples should be obtained every 3 months (+/- 2 weeks) from start of ctDNA surveillance:
 - o ctDNA analysis: 4 x 10 ml collected in ctDNA preservation tubes
- Disease recurrence patients should be followed-up in line with standard practice every 6 months (+/- 1 month) from the start of ctDNA surveillance

Note: The baseline blood sample for ctDNA surveillance should be taken **within 4 weeks** of notification from the ICR-CTSU that the patient is eligible for ctDNA surveillance or **within 4 weeks** of completing standard adjuvant treatment, including adjuvant chemotherapy, whichever occurs later, except for patients receiving adjuvant capecitabine. In this case, the first blood sample should be taken 3 months +/- 2 weeks after the patient commenced capecitabine treatment. If the patient discontinues capecitabine permanently within the first 3 months for reasons other than disease recurrence, the first ctDNA surveillance blood sample should be provided within **4 weeks** of stopping treatment. Patients may start ctDNA surveillance prior to, and during, adjuvant radiotherapy.

8.1.4. Follow up post ctDNA surveillance

Following completion of ctDNA surveillance, patients who were not allocated to the pembrolizumab treatment group should continue to be followed up in line with standard practice at 6 monthly intervals (+/-1 month) until disease recurrence, unless the patient specifically withdraws consent for follow up (see section 12) or until the ICR-CTSU confirms to the recruiting sites that no further follow up is required. This can be done by a telephone call with the patient.

ICR-CTSU

8.2. Schedule of assessments for registration and ctDNA surveillance

	Screening for registration	Registration		ctDNA surveillance (months)							Follow up	
	Screening		0	3	6	9	12	15	18	21	24	Every 6 months thereafter until disease recurrence
Assessments & procedures	Day-28 to Day -1			±2w	± 2w	±2w	±2w	±2w	± 2w	± 2w	± 2w	+/- 1 month
		S	tudy As	sessme	ents							
Written informed consent ¹	Х											
Inclusion/exclusion criteria	Х											
Demographics and medical history	Х											
Concomitant medication review	Х											
Eligibility confirmation	Х											
ECOG performance status	Х											
Disease recurrence ²					Х		Х		Х		Х	Х
		Tumour Tissu	ie & Res	search I	Blood C	ollectio	n					
Additional ctDNA blood sample ³		Х										
Blood sample for ctDNA analysis ⁴			X ⁵	Х	Х	Х	Х	Х	Х	Х	Х	
Archival tumour tissue samples ⁶		Х										

1. Written informed consent should be obtained from the patient for registration in the c-TRAK TN trial prior to conducting any protocol required assessments and procedures (unless required as part of standard patient care).

2. Patients should be followed-up in line with standard practice every 6 months (+/- 1 month) from start of ctDNA surveillance. During follow up post ctDNA surveillance this may be done by a telephone call to the patients. A recurrence tumour tissue sample should be provided at relapse for each patient who has tissue available from a biopsy taken routinely as part of standard patient care.

3. At trial registration, 4 x 10ml blood samples collected in ctDNA preservation tubes for germline DNA and additional ctDNA analysis.

4. 4 x 10ml of blood collected in ctDNA preservation tubes every 3 months (+/- 2 weeks) for up to 2 years from starting ctDNA surveillance. Patients must have completed standard treatment including adjuvant chemotherapy, except capecitabine, before starting ctDNA surveillance. Patients may start ctDNA surveillance prior to, and during, adjuvant radiotherapy.

- 5. The first blood sample for ctDNA surveillance should be taken within 4 weeks of notification from the ICR-CTSU that the patient is eligible for ctDNA surveillance or within 4 weeks of completing standard adjuvant treatment, including adjuvant chemotherapy, whichever occurs later, except for patients receiving adjuvant capecitabine. In this case, the first blood sample should be taken 3 months +/- 2 weeks after the patient commenced capecitabine treatment. If the patient discontinues capecitabine permanently within the first 3 months for reasons other than disease recurrence, the first ctDNA surveillance blood sample should be provided within 4 weeks of stopping treatment. Patients may start ctDNA surveillance prior to, and during, adjuvant radiotherapy.
- 6. Two archival tumour tissue samples either from diagnostic biopsy or primary surgery.

9. RANDOMISATION (PRIOR TO PROTOCOL V6.0) AND TREATMENT ALLOCATION

Prior to the implementation of protocol v6.0 during the original randomised component of the trial, The ICR-CTSU would perform the randomisation independently of the treating team. Each randomised patient was assigned a unique Trial ID.

Where a patient was randomised and allocated to the pembrolizumab treatment group, the ICR-CTSU notified the relevant staff members including the Principal Investigator at the recruiting site and would confirm the patient's unique Trial ID. Where a patient was randomised to the observation group (continued blinded ctDNA surveillance), the treating team and patient were not informed and patients would continue with 3 monthly blinded ctDNA surveillance for up to 2 years (from start of ctDNA surveillance) in an identical manner to those who have remained ctDNA negative.

Following the implementation of protocol v6.0 whereby patients transfer to the non-randomised component of the trial, a patient is allocated to the pembrolizumab treatment intervention and the ICR-CTSU will notify the relevant staff members (including the Principal Investigator) at the recruiting site and will confirm the patient's unique Trial ID.

Patients not receiving adjuvant capecitabine should be invited to confirm consent for the therapeutic part of c-TRAK TN, i.e. pembrolizumab treatment (see section 9.1).

If a patient is receiving adjuvant capecitabine when allocated to pembrolizumab treatment, the same process of informing the site is followed. The patient should be asked if they agree to switch their treatment from capecitabine to pembrolizumab if they are found to be eligible for the therapeutic part of the c-TRAK TN trial (see section 9). If the patient agrees in principle to switch their treatment, they should be invited to confirm consent for the therapeutic part of c-TRAK TN, i.e. pembrolizumab treatment.

Note: Patients who are allocated to pembrolizumab but do not wish to switch current treatment from capecitabine, will not be able to join the therapeutic component of the c-TRAK TN trial and should instead be treated as per the protocol for patients continuing on ctDNA surveillance.

If consent is obtained, the eligibility checks and pre-treatment assessments can then be carried out (see section 11.1). Once these checks have been completed the ICR-CTSU should be informed following the procedure in section 9.3.

9.1. Procedure for obtaining informed consent for pembrolizumab treatment

Patient consent for starting pembrolizumab treatment must be obtained following confirmation from ICR-CTSU that the patient has been allocated to the pembrolizumab treatment group.

The Principal Investigator (or designated investigator) must ensure that each patient is fully informed about the nature and objectives of the trial and possible risks associated with pembrolizumab treatment.

The patient should be given the current ethics approved **c-TRAK TN patient information sheet for pembrolizumab treatment** for their consideration. Patients should only be asked to confirm consent to the trial after they have had sufficient time to consider the implications of a positive ctDNA result, the rationale for accepting pembrolizumab treatment and had the opportunity to ask any further questions.

No further protocol required assessments, other than those required as part of the ctDNA surveillance and standard patient care, should be conducted until the **c-TRAK TN consent form for pembrolizumab treatment** has been signed and dated by both the patient and the investigator at the recruiting site.

Confirmation of the patient's consent and the informed consent process should be documented in the patient's medical notes. A copy of the signed consent form should be provided to the patient and the original retained in the investigator site file, which must be made available for verification by ICR-CTSU trial staff or for regulatory inspection at any time.

9.2. Eligibility criteria for pembrolizumab treatment group

Patients allocated to the pembrolizumab treatment group will be considered eligible to start pembrolizumab treatment only if they fulfil all the inclusion and none of the exclusion criteria listed below. Eligibility should be checked and pre-treatment assessments carried out once allocation to the pembrolizumab treatment group has been confirmed by ICR-CTSU and patient consent to start treatment has been obtained.

9.2.1. Inclusion Criteria

- 1) Signed Informed Consent Form for pembrolizumab treatment
- 2) ECOG performance status 0, 1 or 2
- 3) Adequate organ function as defined by:
 - a. Bone marrow function: ANC \geq 1.5 x 10⁹/L; platelets >100 x 10⁹/L; haemoglobin >9g/dL
 - b. Hepatic function: aspartate aminotransferase(AST) and alanine aminotransferase (ALT) $\leq 2.5 \text{ x upper limit of normal ULM+N}$; bilirubin $\leq 1.5 \text{ x ULN}$; albumin $\geq 2.gmg/dL$
 - c. Renal function: serum creatinine \leq 1.5 x ULN OR estimated GFR (using Cockcroft-Gault)), \geq 60mL/min for patient with creatinine levels > 1.5 x ULN
 - d. Coagulation: $INR \le 1.5 \times ULN$; APTT $\le 1.5 \times ULN$ (unless patient receiving anticoagulation therapy as long as PT or PTT is within therapeutic range of intended use of anticoagulant)
- Women of childbearing potential should have a negative urine or serum pregnancy test within 72 hours prior to receiving the first dose of trial medication. If the urine test is positive or cannot be confirmed as negative, a serum pregnancy test will be required.
- 5) Female and male patients of reproductive potential must be willing to use an adequate method of contraception (appendix 2), starting with the first dose of pembrolizumab through 120 days after the last dose of pembrolizumab. *Note: Abstinence is acceptable if this is the usual lifestyle and preferred contraception for the patient.*
- 6) Patients willing to receive a 12 month course of pembrolizumab and have frequent blood tests (every 3 weeks during treatment and every three months for a year following completion of pembrolizumab treatment).
- 7) No evidence of distant metastatic disease or local recurrence on staging scans conducted at any time since initial diagnosis.

9.2.2. Exclusion Criteria

1) Any concurrent or planned anti-cancer treatment since completing standard therapy for early stage triple negative breast cancer other than loco regional adjuvant radiotherapy or standard adjuvant chemotherapy, or a permitted bisphosphonate/denosumab.

- 2) Diagnosis of an additional cancer since enrolment in the trial other than basal cell carcinoma of the skin or cervical carcinoma in situ.
- 3) Prior chemotherapy, targeted small molecule therapy or radiation therapy within 4 weeks prior to first administration of pembrolizumab, with the exception of planned loco regional adjuvant radiotherapy.
- 4) Prior anti-cancer monoclonal antibody (mAb) within 4 weeks prior to first administration of pembrolizumab.
- 5) Has not recovered (≤ Grade 1 or patient's baseline) from adverse events due to a previously administered therapy. Note: Patients with ≤ grade 2 neuropathy or alopecia of any grade are an exception to this criterion and may qualify for the trial. If patient received major surgery, they must have recovered adequately from the toxicity and/or complications from the surgery prior to allocation.
- 6) Treatment with an unlicensed or investigational product within 4 weeks prior to first administration of pembrolizumab.
- 7) Active autoimmune disease requiring systemic therapy in the last 2 years (i.e. with use of disease modifying agents, corticosteroids or immunosuppressive drugs). Replacement therapy (e.g. thyroxine, insulin or physiologic corticosteroid replacement therapy for adrenal or pituitary insufficiency) is not considered a form of such systemic treatment.
- 8) Diagnosis of immunodeficiency or is receiving systemic steroid therapy or any other form of immunosuppressive therapy within 7 days prior to the first administration of pembrolizumab.
- 9) Known history of active Tuberculosis Bacillus (TB).
- 10) Known history of Human Immunodeficiency Virus (HIV).
- 11) Known active Hepatitis B or Hepatitis C.
- 12) Known history of, or any evidence of active, non-infectious pneumonitis.
- 13) Active infection requiring systemic therapy.
- 14) Previous solid organ or allogenic stem cell transplantation.
- 15) Received a live vaccine within 30 days of planned start of pembrolizumab (seasonal flu vaccines are generally inactivated and are permitted; however intranasal influenza vaccines (e.g. Flu-Mist) are live attenuated vaccines and are not permitted).
- 16) Presence of any systemic illness incompatible with participation in the clinical trial or inability to provide written informed consent.
- 17) Females who are pregnant or breastfeeding.

9.3. Procedure for confirming patient eligibility to start pembrolizumab treatment

If the patient is confirmed eligible to start pembrolizumab treatment, then treatment should commence within a maximum of 4 weeks of the date when the recruiting site was first notified about the treatment allocation. For patients who are switching treatment from capecitabine to pembrolizumab, a washout period of 4 weeks must be observed prior to starting trial treatment. This period may be extended if delays are

encountered for practical reasons including those caused by the COVID 19 pandemic and the patient remains eligible per protocol, please discuss such cases with the ICR-CTSU trial team.

Patients who are ineligible to start treatment due to macroscopic disease identified on pre-treatment imaging will not receive treatment within the c-TRAK TN trial and will instead be treated as per local guidelines for metastatic disease/recurrence. No further blood samples for ctDNA analysis should be collected.

Patients who do not meet the eligibility criteria (for reasons other than disease recurrence) or do not wish to receive pembrolizumab treatment, should continue to have bloods taken for ctDNA surveillance every 3 months for up to 2 years from starting ctDNA surveillance. Patients should then be followed up for disease recurrence detection as described in section 11.5.

The **pre-treatment eligibility checklist** must be completed for all patients allocated to pembrolizumab treatment to confirm patient consent and eligibility and the planned start date of treatment (where applicable). The pre-treatment eligibility checklist should be completed within 4 weeks of when the recruiting site was first notified about the treatment allocation. Written confirmation that eligibility has been assessed by an investigator and confirmation of the patient's consent and the informed consent process should be documented in the patient's medical records.

For patients confirmed eligible, pembrolizumab treatment should commence as soon as possible and within a maximum of 4 weeks from when the recruiting site was first notified about the treatment allocation. As stated above, for patients receiving capecitabine a 4 week washout is required. The trial assessments that should be performed before, during and after pembrolizumab treatment are detailed in section 11.

10. BIOLOGICAL SAMPLE PROCEDURES FOR PEMBROLIZUMAB TREATMENT GROUP

10.1.1. ctDNA blood sample collection during pembrolizumab treatment

Patients receiving pembrolizumab treatment will have blood samples for ctDNA analysis taken pre-dose on Day 1 of each 3 week cycle (-72 hours). Note that for patients receiving pembrolizumab treatment a reduced volume of 20ml (2 x 10ml) blood will be taken.

Following completion of pembrolizumab treatment, blood samples for ctDNA surveillance (2x 10ml) should be taken every 3 months (+/- 2 weeks) from start of ctDNA surveillance for a further 12 months or until disease recurrence (see section 11.5). For patients who have clinical recurrence whilst on pembrolizumab see section 13.

ctDNA blood samples should be sent to the c-TRAK TN central laboratory for mutation analysis. The results of any ctDNA analyses performed during and after pembrolizumab treatment will not be provided to the treating team or patient. If a blood sample is of insufficient quality for analysis, ICR-CTSU will contact the treating team to request that a further blood sample is collected and sent to the c-TRAK TN central laboratory. In such a case, the patient should be invited to attend the clinic as soon as possible in order to provide another blood sample.

Further details regarding the collection of blood samples for ctDNA analysis are given in the c-TRAK TN Investigator Laboratory Manual.

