Prior to the implementation of protocol v6.0 during the randomised component of the trial, if a patient was randomised to the observation group, the treating team and patient were **not** informed that randomisation had taken place in order to remain blinded to the positive ctDNA result the patient would continue to have blood samples collected for ctDNA analysis as described in section 8.

Following implementation of protocol v6.0, all patients who were previously randomised to observation and remain in ctDNA surveillance will transition to the non-randomised component of the trial following reconsent, and be allocated to pembrolizumab at the next positive ctDNA result.

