4. TRIAL ENDPOINTS

4.1. Primary Endpoints

- 1) Positive ctDNA detection by 12 and 24 months from start of ctDNA surveillance.
- 2) Absence of detectable ctDNA or disease recurrence 6 months (24 weeks) after commencing pembrolizumab.

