7.2.2. Blood sample collection during ctDNA surveillance

At registration, an additional sample for ctDNA surveillance should be taken. This will be analysed and used for surveillance for patients who at the time have completed standard therapy **as defined in section 3.1.**

The baseline blood sample for ctDNA surveillance should be taken within **4 weeks** of notification from the ICR-CTSU that the patient has a trackable mutation and so can commence ctDNA surveillance, or within **4**

c-TRAK TN Protocol

weeks of completing adjuvant chemotherapy, whichever occurs later. However, for patients receiving adjuvant capecitabine, the first ctDNA surveillance sample should be taken 3 months +/- 2 weeks after the patient commenced capecitabine, or after the patient has discontinued capecitabine permanently within the first 3 months if treatment was stopped for reasons other than disease progression. Patients may start ctDNA surveillance prior to, and during, adjuvant radiotherapy.

Subsequent blood samples should be taken every 3 months (+/-2 weeks) for up to 2 years from starting ctDNA surveillance or until disease recurrence, unless the patient is allocated to the pembrolizumab treatment group (see sections 9 and 10).

During ctDNA surveillance, at each visit 40ml (4 x 10ml) blood should be collected in the ctDNA preservative tubes provided. Further details regarding the collection of blood samples for ctDNA analysis are given in the c-TRAK TN Investigator laboratory manual.

If a blood sample is of insufficient quality for analysis, ICR-CTSU will contact the treating team to request that a further blood sample is collected and sent to the c-TRAK TN central laboratory. In such a case, the patient should be invited to attend the clinic as soon as possible in order to provide another blood sample.

7.2.3. ctDNA surveillance results

ctDNA blood samples should be sent to the c-TRAK TN central laboratory for mutation analysis. The results from the ctDNA analyses performed during surveillance will not be provided to the treating team or patient.

Should a patient's blood sample be ctDNA positive within 12 months of starting surveillance, or at registration for patients that have completed standard therapy at the time of registration **as defined in section 3.1**, the c-TRAK TN central laboratory will notify ICR-CTSU and the patient will be allocated to pembrolizumab treatment within the therapeutic trial (see section 9).

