11.3. Prior to each cycle (cycle 2 onwards)

Please see section 11.1 for assessments required prior to the first dose of pembrolizumab (i.e. cycle 1 only). The following assessments should be conducted within 72 hours prior to each cycle (from cycle 2 onwards) of pembrolizumab:

- Concomitant medication review
- Review of adverse events
- Full physical examination (including weight at cycles 4, 8, 12 and 16 only, ECOG performance status, vital signs)
- Safety blood tests: clotting (INR or PT/ aPTT), haematology (ANC, platelets, haemoglobin), biochemistry; hepatic function (bilirubin, ALT, AST, ALP and GGT), renal function (serum creatinine or estimated GFR (using Cockcroft-Gault)), thyroid function (T3, T4 TSH), glucose (random)
- Urinalysis
- ECG (only if clinically indicated)
- Research blood samples for ctDNA analysis:
 - o 2 x 10ml collected in ctDNA preservation tubes taken pre-dose on each cycle
- Research blood samples for PBMC isolation pre-dose **ONLY on cycle 3** (PBMC sites only)
 - 3 x 10ml collected in heparin tubes, to be couriered same day as per the c-TRAK TN Investigator Laboratory Manual.

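### ctDNA positivity is called on 40 ml of blood but clearance on pembrolizumab on 20 ml; unless assay input is equalised, the primary clearance rate is biased upward, by an amount the protocol does not let one derive

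*Protocol*

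**What the plan says.** **Surveillance.** Protocol 7.2.2 sets the volume for the samples that can trigger allocation: "During ctDNA surveillance, at each visit 40ml (4 x 10ml) blood should be collected". Section 8.1.3 and the schedule in 8.2 give the same volume.

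**On pembrolizumab.** Section 10.1.1 halves it: "Note that for patients receiving pembrolizumab treatment a reduced volume of 20ml (2 x 10ml) blood will be taken". Section 11.1 specifies 2 x 10 ml before the first dose, and 11.3 repeats it from cycle 2 onwards: "2 x 10ml collected in ctDNA preservation tubes taken pre-dose on each cycle".

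**Observation group.** Section 3.2.2 says "the patient would continue to have blood samples collected for ctDNA analysis as described in section 8", and section 8.1.3 specifies "ctDNA analysis: 4 x 10 ml collected in ctDNA preservation tubes". Section 9 adds that these patients continued "in an identical manner to those who have remained ctDNA negative".

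**Endpoint.** Section 4.1 defines the therapeutic primary endpoint as "Absence of detectable ctDNA or disease recurrence 6 months (24 weeks) after commencing pembrolizumab". Section 19.3.1 turns this into a proportion, with no condition on blood volume, plasma volume or DNA input.

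**Interpretation.** Section 19.1.2 reads clearance as evidence of drug activity, because no patient with ctDNA detected at baseline cleared it spontaneously in earlier research. It looks to the observation group for further support of that reading.

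**The concern.** Section 1.1 notes that ctDNA is a small fraction of circulating DNA and needs highly sensitive assays. When few mutant molecules are present, halving the sample halves the expected number captured. Entry is then decided by the more sensitive test and loss of positivity by the less sensitive one. A patient whose ctDNA has not changed can move from positive to negative because less blood was examined, and the endpoint would count that as clearance if there is no recurrence.

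The inference from clearance to activity requires a negative result to mean the same at both times. The observation group cannot check this, because its volume was never reduced: few spontaneous negatives at 40 ml would say nothing about volume-driven negatives at 20 ml. Volumes may also be mixed inside the primary analysis. Under the intention-to-treat rule in 19.4, allocated patients who never start pembrolizumab are included, and 9.3 keeps those without recurrence on surveillance sampling.

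**Working it through.** **1. The plan's own rule.** Section 19.1.2 uses an A'Hern single-stage design with alpha 0.1, power 90% and p0 = 0.30. In the main scenario 30 patients receive pembrolizumab, p1 = 0.54 and 13 successes are required. Exact binomial:
- P(X ≥ 13 | n = 30, p = 0.30) = 0.084
- P(X ≥ 13 | n = 30, p = 0.54) = 0.912

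The rule reproduces.

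**2. Which sample decides.** Cycles last 21 days, so 24 weeks after cycle 1 day 1 is the pre-dose visit of cycle 9 (8 x 3 = 24), and week 21 is cycle 8. Both are 20 ml draws under 10.1.1 and 11.3.

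**3. Effect of halving the volume.** All inputs in this step are assumptions; the protocol gives no copy number, plasma volume, DNA input or call threshold. Assume all blood drawn is assayed, mutant molecules are Poisson with mean λ in 40 ml and λ/2 in 20 ml, one molecule gives a positive call, and ctDNA is unchanged.
- P(negative at 40 ml) = exp(−λ) = f
- P(negative at 20 ml) = exp(−λ/2) = √f

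| Detection at 40 ml | f | √f | Detection at 20 ml |
|---|---|---|---|
| 90% | 0.10 | 0.316 | 68% |
| 80% | 0.20 | 0.447 | 55% |

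If two molecules are needed, 80% at 40 ml becomes 44% at 20 ml.

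Dependence on copy number, one-molecule call:

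| λ per 40 ml | Negative at 40 ml | Negative at 20 ml | Excess |
|---|---|---|---|
| 2 | 0.135 | 0.368 | 0.233 |
| 3 | 0.050 | 0.223 | 0.173 |
| 5 | 0.007 | 0.082 | 0.075 |
| 10 | <0.001 | 0.007 | 0.007 |

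The effect is material at a few copies per 40 ml and negligible from about 10.

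**4. Effect on the decision rule.** Further assumptions: true clearance 0.30, and 20% of non-clearers are low-level, each detectable with probability 80% at 40 ml. Apparent clearance = 0.30 + 0.70 x 0.20 x P(negative).

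| Assay at week 24 | P(negative) | Apparent clearance | P(≥ 13 of 30) |
|---|---|---|---|
| Perfect | 0 | 0.300 | 0.084 |
| 40 ml | 0.200 | 0.328 | 0.151 |
| 20 ml | 0.447 | 0.363 | 0.266 |

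The part due to volume is the step from 15% to 27%. The step from 8% to 15% is imperfect sensitivity that would exist at 40 ml as well.

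**5. Effect of growth.** If ctDNA in the low-level patients doubles by week 24, the mean in 20 ml is again λ, so the miss rate is back to the 0.20 of the entry draw. If it rises four-fold, the miss rate at 20 ml is 0.20² = 0.04, apparent clearance is 0.306 and P(≥ 13 of 30) is 0.096.

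**6. A wholly inactive drug.** With no true clearance and the same inputs, apparent clearance at 20 ml is 0.20 x 0.447 = 0.089, and P(≥ 13 of 30) is below 0.000001. Only if every patient sat near the detection limit without recurrence would this change: at λ = 2 for all, the probability is 0.286 at 20 ml and 0.0001 at 40 ml.

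**The case against.** **Volume drawn is not volume assayed.** The protocol fixes the draw and refers sampling details to a laboratory manual that is not shown. If that manual sets a common plasma or DNA input, the bias shrinks or vanishes. This stands. A reader might infer that the endpoint does credit lost sensitivity as drug effect; the document supports only that it may, because nothing in it equalises input.

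**Unchanged ctDNA over six months fits the trial's disease model poorly.** Section 9.3 allows up to 4 weeks from notification to treatment, so week 24 can fall about 28 weeks after notification. Section 1.1 cites a median lead time of 7.1 months (about 31 weeks), and 1.2.1 describes recurrence after detection as nearly inevitable. A non-responder may have rising ctDNA, or may have recurred and counts as a failure whatever the blood shows. This also stands, and it limits the size. It does not cover patients whose ctDNA is held low but not cleared.

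**The observation group is not a formal comparator.** Section 19.1.2 calls it a reference control, and its clearance is reported with its own confidence interval. A reader might infer that a between-group test is invalidated; no such test of clearance is planned. What remains is that this reference cannot detect volume-driven negatives.

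**The p0 of 0.30 leaves margin.** It does, as step 6 shows, although the protocol does not justify p0 on that ground.

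**One time point for sustained clearance.** The endpoint is explicitly defined at 24 weeks, and alternative clearance definitions are exploratory, so this is not an error.

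**Conclusion.** The mismatch is plain in the text: 40 ml for positivity, 20 ml for clearance on treatment, 40 ml in the observation reference. If assay input follows the draw, the bias can only raise the apparent clearance rate.

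Its size cannot be derived from the protocol. The illustration of 15% rising to 27% rests on Poisson sampling, a one-molecule call, all blood being assayed, unchanged ctDNA, true clearance exactly at p0, and an assumed fifth of non-clearers being low-level. Two stronger readings are not supported. The whole gap from 8% to 27% is not due to volume, and under the same inputs an inactive drug would not pass the rule.

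This is a moderate point about a cheap, avoidable, one-directional bias in the primary endpoint. It is not a flaw that must stop the trial or void the analysis.

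**What to change.** **Going forward.** In 10.1.1 and 11.3 (and 11.1 for cycle 1), collect 4 x 10 ml at the existing 24-week pre-dose visit and at cycle 1 pre-dose. Alternatively, analyse the same plasma or DNA input at entry, at week 24 and in the observation group, and say so in 19.3.1. If input is already equalised, that one sentence closes the point.

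**Patients already past week 24.** Add two volume-matched sensitivity analyses of the primary endpoint using existing samples:
- clearance among patients positive on the 20 ml cycle 1 pre-dose sample;
- clearance requiring both the week-21 and the week-24 20 ml samples to be negative.

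The two-sample rule should stay a sensitivity analysis, because as the primary definition it would change the endpoint: a patient who clears between weeks 21 and 24 would become a failure. It also matches 40 ml exactly only for a one-molecule call. With a two-molecule call and 80% detection at 40 ml, it misses 31%, against 56% for one 20 ml sample and 20% for 40 ml.

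**Cost.** Two extra tubes at one or two existing draws, mixed volumes between earlier and later patients, and a slightly lower apparent clearance rate.
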